#### 8.2.4 Two-step Cox model

The two-step Cox model [Anderson 1982] is an extension of the conventional Cox model allowing for different treatment effects in different time intervals. The conventional Cox model comparing two treatments vs placebo can be fitted using the SAS® statements like:

```
proc phreg data=<data>;  
  model t*e(0)=treat1 treat2/ risklimits ties=breslow;  
run;
```

Here *treat1* and *treat2* are treatment indicators (*treat1* = 1 for treatment 1, 0 otherwise; *treat2* = 1 for treatment 2, 0 otherwise; placebo will have *treat1* = *treat2* = 0), *t* is the time to event and *e* is an event indicator (1 = event; 0 = no event). The treatment effects are exponentiated to become hazard ratios vs placebo and by using *risklimits* their 95% CIs are obtained.

In the two-step Cox model the time axis is divided in two time intervals  $0 < t \leq C$  and  $t > C$  where the value of *C* is pre-specified. It can be fitted using SAS® statements like:

```
proc phreg data=<data>;  
  model t*e(0)=treat11 treat12 treat21 treat22/ risklimits  
  ties=breslow;  
  treat11=treat1*(t<=C);  
  treat12=treat1*(t>C);  
  treat21=treat2*(t<=C);  
  treat22=treat2*(t>C);  
run;
```

Here *treat11* and *treat12* are time-dependent covariates indicating the effect of treatment 1 in the first ( $t \leq C$ ) and second ( $t > C$ ) interval, respectively. Similarly, *treat21* and *treat22* indicate the effect of treatment 2 in the first and second interval, respectively.

In this study the two intervals are the SB and the DB aprocitentan part, respectively, so  $C = 28$  days. (*C* may be fine-tuned on a subject level using the DB treatment end day [see Section 10.1.1]). The two-step Cox model gives hazard ratios for aprocitentan 12.5 mg vs placebo and aprocitentan 25 mg vs placebo for the DB part as well as the SB aprocitentan part in a single analysis. Note that in the latter part all subjects receive aprocitentan 25 mg, so an analysis based on treatment in the preceding DB part is somewhat artificial. However,

the two-step Cox model ensures that all events are included in the analysis and enables the assessment of ‘prolonged’ treatment effects (if any).

### 8.2.5 Control/response analysis

This analysis will be implemented by the following SAS® statement:

```
proc freq;  
  tables treatment*response / nocol nopercnt cmh1 commonriskdiff;  
run;
```

For DB-WD the analysis should be stratified by DB treatment, so treatment in DB (trt01pn) needs to be added in the tables statement.

## 9 INTERIM ANALYSES

No interim analysis will be performed.

## 10 GENERAL DEFINITIONS AND DERIVATIONS

**Baseline** is defined as the last available measurement before or on the day of randomization. The date and time of randomization are taken from the **IXRS Subject eCRF**.

**DB-WD baseline** (Week 36) is defined as the last available measurement before or on the day of Re-randomization. The date and time of re-randomization are taken from the **IXRS Subject eCRF**.

If both date and time of the measurement are collected, baseline is the last measurement up to the date and time of randomization. If only the date is collected, baseline is the last measurement before the date of randomization.

### 10.1 Analysis periods and visit windows

#### 10.1.1 Analysis periods

The **screening period** is defined as the time from the informed consent date until one day before the run-in period start date (or EOS if the subject does not enter the run-in).

The **RI period** begins at the date of the first dose of RI treatment and ends at the date of the last dose of RI treatment, collected on the **Study Treatment Log** where ‘Study Period’ is ‘Single Blind Run-in’.

The **randomized treatment period** begins at the DB treatment start date and ends at the *last* of the treatment stop dates collected on the **Study Treatment Log** where ‘Study Period’ is not ‘Single Blind Run-in’ and the reason for treatment end is not ‘Interruption due to an AE’ or ‘Interruption not due to an AE’.

The randomized treatment period is divided into three parts: DB, SB aprocitentan and DB-WD.

- The DB part begins at the DB treatment start date and ends at the DB treatment stop date collected on the **Study Treatment Log** where ‘Study Period’ is ‘Double-Blind Treatment (Part 1)’ and the reason for treatment end is not ‘Interruption due to an AE’ or ‘Interruption not due to an AE’.
- The SB aprocitentan part begins at the SB treatment start date and ends at the SB treatment stop date collected on the **Study Treatment Log** where ‘Study Period’ is ‘Single-Blind Treatment (Part 2)’ and the reason for treatment end is not ‘Interruption due to an AE’ or ‘Interruption not due to an AE’.
- The DB-WD part begins at the DB-WD treatment start date and ends at the DB-WD treatment stop date collected on the **Study Treatment Log** where ‘Study Period’ is ‘Double-Blind Withdrawal Treatment (Part 3)’ and the reason for treatment end is not ‘Interruption due to an AE’ or ‘Interruption not due to an AE’.

Should there be any ‘gap’ between the end of one period and the start of the next, then the gap days are allocated to the former period. In the unlikely case that the gap is more than 30 days, gap days 31, 32, etc. will not be allocated to a study part.

The **safety FU period** begins one day after the end of the randomized treatment period and ends at the date of the EOS visit. Safety data obtained during the safety FU period or at the EOS visit will be allocated to the last part of the subject’s randomized treatment period. This is restricted to data collected up to EOT+30 days. Safety data collected beyond that time point will not be allocated to a study part.

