 Study treatment including standardized background antihypertensive therapy should be brought back at each visit for drug accountability (pill counts).

 All AEs and SAEs that occur after signing the informed consent form and up to 30 days after study treatment discontinuation must be reported.

 Randomized subjects who prematurely discontinue prior to Week 48/Visit 15 should have an EOT visit scheduled no later than 7 days after the last dose of randomized study treatment.

 For subjects who discontinued during the RI period, this will be a phone call to collect adverse events and concomitant medications only.

ABPM = ambulatory blood pressure monitoring; AE = adverse event; AOBPM = automated office blood pressure measurement; BP = blood pressure; DB = double-blind; ECG = electrocardiogram; EOS = End-of-Study; EOT = End-of-Treatment; FU = follow-up; HR = heart rate; NT-proBNP = N-terminal pro-brain natriuretic peptide; PK = pharmacokinetic(s); RI = run-in; SAE = serious adverse event; SB = single-blind; UACR = urine albumin-to-creatinine ratio; WD = withdrawal.

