## 7.3 Laboratory tests

### 7.3.1 Variables

Laboratory assessments are performed according to the schedule of assessments [Table 1 and Table 2]. Laboratory data are evaluated in SI units as provided by the central laboratory. The following tests are considered:

- Hematology: hemoglobin, hematocrit, erythrocyte count, reticulocyte count, leukocyte count with differential counts, platelet count, mean corpuscular volume.
- Clinical Chemistry: aminotransferases (aspartate aminotransferase [AST] / alanine aminotransferase [ALT]), alkaline phosphatase, bilirubin and direct bilirubin, cholesterol, triglyceride, high density lipoprotein, low density lipoprotein, creatinine, eGFR (estimated using the CKD-EPI creatinine equation), urate, albumin, protein, glucose, sodium, potassium.
- Urinalysis: UACR.

For women of childbearing potential, urine as well as serum pregnancy tests are performed, but these results will not be summarized as part of the laboratory data. Positive pregnancy tests (if any) will be reported.

Results of local laboratory tests (collected on the **Local Laboratory Hematology** and **Local Laboratory Clinical Chemistry** eCRF) will not be used in summaries but will be listed.

Laboratory marked abnormalities are defined in Section 14.2. When determining double-blind treatment-emergent marked laboratory abnormalities, all assessments (including the unscheduled ones) are considered.

All assessments (including the unscheduled ones) are considered and re-assigned to the most appropriate visit according to the rules described in Section 10.1.2.

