### 7.3.2 Analysis

Changes from baseline for laboratory tests to visits in the DB+SB part will be summarized using descriptive statistics by visit and treatment group (in the DB part). Changes from DB-WD baseline (Week 36) to visits in the DB-WD part and up to EOS will be summarized by visit and treatment group (in the DB-WD part). Data will be displayed in SI units whenever possible and graphical approaches will be applied for certain variables.

Percentage changes from baseline in plasma volume to visits in the DB+SB part will be estimated based on baseline (V4) as well as post-baseline (Vx) in hemoglobin and hematocrit (as a fraction between 0 and 1) using the following formula [[Strauss 1951](#)]:

$$\text{estimated change} = 100 \times \frac{\text{hemoglobin (V4)}}{\text{hemoglobin(Vx)}} \times \frac{1 - \text{hematocrit (Vx)}}{1 - \text{hematocrit(V4)}} - 100$$

Percentage changes from Week 36 (V11) in plasma volume to visits in the DB-WD part will be estimated similarly but with V4 replaced by V11. Estimated changes in plasma volume will be summarized by visit and treatment group (in the DB+SB part or DB-WD part, where appropriate).

The number (%) of subjects with laboratory marked abnormalities will be tabulated by study part (DB, SB, and DB-WD) and treatment group (within study part). In addition, the number (%) of subjects with AST or ALT > 3 × the ULN combined with bilirubin > 2 × ULN will be tabulated. In addition, AST or ALT > 5 or 10 × ULN will also be tabulated.

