### 10.1.2 Visit windows

For visit-based variables (for visits see schedule of assessments in [Table 1](#) and [Table 2](#)), analysis windows are based on study day numbers defined as follows:

**Study day** is defined for the entire study as assessment date minus randomization date plus 1 day. Thus, the day of randomization is study Day 1. For dates prior to randomization, study day is the negative number of days between the date under consideration and the date of randomization. Thus, the day before randomization date is study Day –1. Study Day 0 does not exist.

**Withdrawal (WD)** day is defined for the DB-WD part as assessment date minus re-randomization date plus 1 day. If a subject is not re-randomized, then WD day is not defined.

The analysis windows around the visits are given in [Table 6](#). For efficacy variables (except for ABPM measurements) and safety analyses the windows are based on study or WD days and on the start and stop dates of the study parts defined above.

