**Table 6 Visit windows**

Visit	Target		Efficacy		Safety	
	Study day	WD day	Lower a	Upper a	Lower a	Upper a
DB part						
4 (Randomization)	1	-		1		1
5 (Week 2)	14	-	8	20	2	20
6 (Week 4)	28	-	21	36 b	21	36 b
SB aprocitentan part						
7 (Week 6)	42	-	37 c	62	37 c	62
8 (Week 12)	84	-	63	111	63	111
9 (Week 20)	140	-	112	167	112	167
10 (Week 28)	198	-	168	223	168	223
11.1 (Week 36)	252	-	224	258 d	224	258 d
DB-WD part						
11.2 (Re-randomization)	-	1		1		1
12 (Week 38)	266	14	8	20	2	20
13 (Week 40)	280	28	21	41	21	41
14 (Week 44)	308	56	42	69	42	69
15 (Week 48)	336	84	70	97	70	97 e
EOS (EOT + 30 days)	366	114	NA	NA	98	

a vs study day for the DB part and vs WD day for DB-WD part. b Or end of DB treatment part + one day (whichever comes first). c But not before start of SB aprocitentan part (whichever comes first). d Or end of SB aprocitentan part + one day (whichever comes first). e Or end of DB-WD treatment part + one day (whichever comes first).  
 DB = double-blind; NA=Not applicable; WD = withdrawal.

If there is more than one value within the same visit window, the value closest to the planned assessment date will be taken. Where multiple assessments fall on the same day or have the same visit label, then the latest in time is used (or with the highest SDTM sequence number, if time is not collected). In the event of equidistant values from the planned time point, the last assessment will be considered for the analyses. If there are records ‘on-treatment’ and ‘off treatment’ within the same visit window, use only those ‘on-treatment’.

If measurements involve time, the following target times should be considered:

- Target day/time = Target day and time 12:00
- Lower day/time = Lower day and time 0:00
- Upper day/time = Upper day and time 23:59

AOBPM measurements (efficacy) will also have indicator whether the measurement was ‘on-treatment’. A measurement is considered on-treatment if it was taken before or within one day of the end of the randomized treatment period (defined above).

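### Read literally, most Table 6 safety windows stay open after treatment stops and the EOS row opens too late, so off-drug follow-up values can enter intermediate visits or no visit at all

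*SAP*

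**What the plan says.** - **Allocation (SAP 10.1.1).** Safety data "obtained during the safety FU period or at the EOS visit will be allocated to the last part of the" subject's randomised treatment period. The next sentence limits this: "This is restricted to data collected up to EOT+30 days". Later data belong to no study part.
- **Re-assignment (SAP 7.3.1; the same for weight and pulse in 7.5.1).** All laboratory assessments, unscheduled ones included, "are considered and re-assigned to the most appropriate visit according to the rules described in Section 10.1.2".
- **Closing limits (SAP Table 6, safety columns).** Week 48 carries footnote e: "Or end of DB-WD treatment part + one day (whichever comes first"). Footnotes b and d do the same for Weeks 4 and 36. Weeks 2, 6, 12, 20, 28, 38, 40 and 44 have fixed upper day limits only; footnote c touches only the lower limit of Week 6.
- **EOS row (SAP Table 6).** The safety window opens at WD day 98 with no upper limit. Section 10.1.2 leaves WD day undefined for subjects who are not re-randomised.
- **Promised output (SAP 7.3.2; similarly 7.5.2).** Changes from DB-WD baseline "to visits in the DB-WD part and up to EOS will be summarized by visit and treatment group".
- **General sentence (SAP 10.1.2).** For efficacy variables other than ABPM, and for "safety analyses the windows are based on study or WD days and on the start and stop dates of the study parts defined above".
- **Schedule (SAP Table 2).** Laboratory tests, weight and AOBPM (which yields pulse) are marked at follow-up; ECG appears not to be. EOS is at Day 366 with a +3-day window. Subjects who stop early "should have an EOT visit scheduled no later than 7 days after the last dose of randomized study treatment".

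**The concern.** The by-visit summaries of haemoglobin, estimated plasma volume, NT-proBNP, renal and liver tests and weight are where a reader sees whether fluid and haemodilution effects appear, persist and reverse. If a value taken 30 days off drug is filed under an intermediate on-treatment visit, a reversible effect is pulled toward zero there. In the DB-WD part the aprocitentan versus placebo contrast shrinks as well. The affected subjects are those who stopped treatment, some of them possibly for these same effects, so the error need not be random.

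The EOS row has the opposite problem. Early DB-WD stoppers, whose off-drug recovery it should show, are missing from it. Finally, a programmer following the table and one following the general sentence in Section 10.1.2 could produce different tables.

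**Working it through.** **The plan's own figure.** EOS is EOT + 30 days: 336 + 30 = study Day 366 and 84 + 30 = WD day 114. Both match Table 6.

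**Assumptions.** Last dose on day L; EOS on day L + 30; scheduled visits on their target days. A window from lo to up with no closing limit then captures stops from L = lo − 30 to up − 30. A window closed at L + 1 can never capture day L + 30.

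| Last dose | EOS falls on | Table 6 safety slot | Stop days |
|---|---|---|---|
| Study Day 29–32 | 59–62 | Week 6 | 4 |
| 33–81 | 63–111 | Week 12 | 49 |
| 82–137 | 112–167 | Week 20 | 56 |
| 138–193 | 168–223 | Week 28 | 56 |
| 194–251 | 224–281 | none (Week 36 closed by d, or past Day 258) | 58 |
| WD day 1–11 | 31–41 | Week 40 | 11 |
| 12–39 | 42–69 | Week 44 | 28 |
| 40–67 | 70–97 | none (Week 48 closed by e; EOS not yet open) | 28 |
| 68–83 | 98–113 | EOS, correctly | 16 |

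So 4 + 49 + 56 + 56 = 165 of 223 SB stop days (74%) and 11 + 28 = 39 of 83 DB-WD stop days (47%) lead to an intermediate visit. These are shares of possible stop days, not of subjects. Weeks 2 and 38 are also left open, but a 30-day EOS value cannot fall in them. DB stops on Days 7–28 put EOS on Days 37–58, inside Week 6 only if footnote c does not exclude subjects who never start SB; Days 1–6 give no slot.

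**Competing EOT value.** Table 6 prefers on-treatment over off-treatment records in one window, and otherwise takes the value closest to target.
- EOT at L + 1: EOS is the only record in its window on 91 of the 165 SB days and all 39 DB-WD days. On the other 165 − 91 = 74 SB days the on-treatment preference, if it applies, displaces EOS. Under the closest-to-target rule alone, EOS is selected on 128 of 165.
- EOT at L + 7: the EOT value is itself off treatment by the one-day definition, so the preference cannot separate the two. The closest-to-target rule selects EOS on 116 of 165 SB days and 37 of 39 DB-WD days.

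**Illustrative size.** Drop-out by part is not reported. Assume constant hazards with 15% of 730 stopping over 252 days and 10% over the 84 DB-WD days, and every stopper attending EOS:
- λ₁ = −ln(0.85)/252 = 0.000645 per day; λ₂ = −ln(0.90)/84 = 0.001254 per day; re-randomised 730 × 0.85 = 620.5.
- Week 20: off-drug 730 × (e^(−81λ₁) − e^(−137λ₁)) = 24.6; on-drug 730 × e^(−140λ₁) = 667.0; share 24.6/691.6 = 3.6%.
- In the same way: Week 12, 22.2/713.7 = 3.1%; Week 28, 23.7/667.0 = 3.6%; Week 40, 8.5/607.6 = 1.4%; Week 44, 21.1/599.5 = 3.5%.
- With half attending: 1.6%, 1.8%, 1.8%, 0.7% and 1.8% at Weeks 12, 20, 28, 40 and 44.
- With the on-treatment preference applied and EOT at L + 1, 29 stop days remain for each of Weeks 12, 20 and 28, and the share falls to 1.9% at each (for Week 20, 12.8/679.8).

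If stoppers would have shown the same mean change as the others and it reverses fully, the visit mean is understated by about these percentages.

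**The case against.** 1. **The general sentence may close every window.** Section 10.1.2 says the windows rest on part start and stop dates as well as day numbers. This is a possible reading, and it makes the matter one of unclear intent rather than proven misallocation. But footnotes b, d and e would then be redundant, and Section 10.1.1 extends the last part to include follow-up data. Nor can the sentence open the EOS row before WD day 98.
2. **The on-treatment preference may cover safety data.** It stands in the general text under Table 6, so this is fair. The indicator, however, is specified only for AOBPM, and the rule acts only when both kinds of record share a window. It reduces the SB problem and leaves Weeks 40 and 44 untouched when EOT is at L + 1.
3. **EOS at +31 to +33 days belongs to no part.** This stands, and it narrows the misfiling. But those values are then allocated to no study part, although they fall within the EOS visit's own window.
4. **The consequence is limited.** This also stands. The by-visit outputs are descriptive. Adverse events and marked laboratory abnormalities are tabulated by study part, not through these windows.

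**Conclusion.** The point holds as a gap in specification with a definite literal consequence. Off-drug laboratory, weight and pulse values can be summarised at Weeks 12, 20, 28, 40 or 44, with Week 6 marginal, and the EOS summary promised for the DB-WD part omits stops before WD day 68. For subjects never re-randomised no EOS summary is promised, so their value is misplaced or unplaced rather than missing from a planned table.

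Three stronger readings are tempting, and the documents do not support them:
- **That all early discontinuers are misfiled.** Stops on study Days 194–251 and WD days 40–67 get no slot, and WD days 68–83 reach EOS correctly.
- **That nearly a tenth of values are off-drug.** The planning figures (600 randomised, 380 re-randomised) would give 50.0/515.5 = 9.7% at Week 20, but SAP Section 2.1 says drop-out was lower than expected.
- **That ECG is affected too.** Table 2 appears to schedule none at follow-up.

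The number of subjects cannot be derived. Under the assumed 15% and 10% drop-out it is at most about 4% of values at a visit, and less if fewer attend EOS or the on-treatment preference applies. The day ranges assume EOS exactly 30 days after last dose; if the 30 days run from a later EOT visit, they move down by that delay. No efficacy test is affected.

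**What to change.** For safety variables only:

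1. Apply the closing limit of footnotes b, d and e (end of the part + one day) to every post-baseline safety window in Table 6. State that the on-treatment preference covers safety data. Add a rule for EOT visits made 2 to 7 days after last dose, which would otherwise fall outside every closed window.
2. Assign the follow-up visit to the EOS row by visit label, for all subjects including those not re-randomised. Step 1 alone does not do this: the row would still take only stops from WD day 68. A label is safer than a day range, because a range starting soon after treatment stop would sweep late EOT visits into EOS.
3. Reconcile step 2 with the EOT + 30-day limit in Section 10.1.1 and the +3-day EOS visit window in Table 2, so that an EOS visit on days 31 to 33 has a stated home.

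The cost is a short edit to Table 6 and Sections 10.1.1 and 10.1.2, plus the derivation program. No new data are needed and the efficacy windows stay as they are. The downside is slightly fewer values at intermediate visits.

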### 7.1 Adverse events

#### 7.1.1 Variables

##### 7.1.1.1 Treatment-emergent adverse events

The original terms used by the investigators to describe AEs in the **Adverse Events** eCRF are assigned a PT and a SOC for classification and tabulation using MedDRA (last available version).

Subjects who experienced the same AE more than once within a specified time period (as qualified by the same PT) are counted only once.

An event/assessment is treatment-emergent if the onset/assessment date is between the start date of the randomized treatment period up to EOT+30 days (begin and end dates included). More in particular:

- An event/assessment is DB treatment emergent if the onset/assessment date is between the start date of the DB part up to the day before the start date of the SB treatment part (or EOT + 30 days if the subject did not enter the SB part);

- An event/assessment is SB treatment emergent if the onset/assessment date is between the start date of the SB aprocitentan part up to the day before the start date of the DB-WD treatment part (or EOT + 30 days if the subject did not enter the DB-WD part);
- An event/assessment is DB-WD treatment emergent if the onset/assessment date is between the start date of the DB-WD part up to EOT + 30 days.

An event/assessment with an onset/assessment date between the start date of the run-in period up to the start of randomized treatment period (if the subject is randomized; EOT if the subject is not randomized) will be designated as run-in-emergent.

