### 7.5.2 Analysis

Descriptive statistics by study part (DB+SB and DB-WD), visit and treatment group (within study part) will be provided for observed values as well as absolute changes from baseline to each visit in the DB and SB parts and from DB-WD baseline (Week 36) to each visit in the DB-WD part and up to EOS for body weight and pulse rate.

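### The SAP stops allocating safety assessments at EOT + 30, the first day Table 2 permits the EOS visit when EOT is on target, so an on-schedule EOS laboratory value can miss the by-part marked-abnormality tables

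*SAP*

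**What the plan says.** SAP 10.1.1 deals with follow-up data in three consecutive sentences. The first is inclusive: "Safety data obtained during the safety FU period or at the EOS visit will be allocated to the last part of the subject’s randomized treatment". The second narrows it: "This is restricted to data collected up to EOT+30 days". The third closes it: "Safety data collected beyond that time point will not be allocated to a study part".

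SAP 7.1.1.1 sets the matching limit for treatment emergence, and it covers assessments as well as events: "An event/assessment is DB-WD treatment emergent if the onset/assessment date is between the start date of the DB-WD part up to EOT + 30 days". Subjects who stop in the DB or SB part have the same EOT + 30 limit.

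Table 2 places EOT (Visit 15) at Day 336 (±4 days) and the follow-up visit at Day 366 (+3 days). Laboratory tests, body weight and AOBPM with pulse are all scheduled at that follow-up visit.

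Table 6 lists EOS in the DB-WD block at study day 366 and WD day 114. Its safety window opens at WD day 98 and has no upper limit.

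Two sections plan by-visit summaries that reach EOS. For laboratory changes, 7.3.2 covers changes from DB-WD baseline "to visits in the DB-WD part and up to EOS will be summarized by visit and treatment group". For vital signs, 7.5.2 runs "to each visit in the DB-WD part and up to EOS for body weight and pulse rate".

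**The concern.** The allocation limit coincides with the earliest on-schedule EOS day instead of covering the visit window. A site that holds the visit one to three days later is fully compliant, yet under 10.1.1 the results belong to no study part and under 7.1.1.1 they are not treatment-emergent.

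The consequence is specific. Marked laboratory abnormalities are counted by study part and treatment group, not by visit; Table 5 shows no visits for them. A liver-enzyme or haemoglobin abnormality first seen at EOS is counted if the visit fell on one permitted day and not if it fell on the next. Table 6 does not help, because it assigns a visit label and not a study part.

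A second uncertainty adds to this. SAP 2.1 uses EOT for a visit at Week 48, whereas 10.1.1 ends the randomized treatment period at the last recorded treatment stop date. The SAP does not say which of the two starts the 30-day count.

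**Working it through.** This is day arithmetic.

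**Inputs**
- EOT target Day 336, window ±4, so Days 332 to 340 (Table 2).
- EOS Day 366, window +3, so Days 366 to 369 (Table 2).
- Week 48 target WD day 84; EOS target WD day 114; EOS safety window from WD day 98, upper limit blank (Table 6).
- Limit for allocation and treatment emergence: EOT + 30 (10.1.1, 7.1.1.1).
- AE reporting: up to 30 days after treatment discontinuation (Table 2, footnote 10).
- Early stoppers: EOT visit no more than 7 days after the last dose (Table 2, footnote 11).

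**1. The plan's own figure.** 336 + 30 = 366 and 84 + 30 = 114. Both match the Table 6 targets.

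**2. EOT at Day 336.** Permitted EOS days minus EOT: 366 − 336 = 30, 367 − 336 = 31, 368 − 336 = 32, 369 − 336 = 33. One of the four days is within the limit and three are beyond it. On the WD scale these are days 114 to 117, all inside Table 6's open EOS window.

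**3. From days to visits.** If a proportion p of visits falls exactly on EOT + 30 and the rest on the other permitted days, the share left out is 1 − p. That is 0% if every visit is on target, 75% if visits are spread evenly over the four days (1 − 1/4), and 100% if none is on target. The documents do not give p.

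**4. EOS fixed by study day, EOT anywhere in its window (assumption).** The interval runs from 366 − 340 = 26 to 369 − 332 = 37 days. There are 9 × 4 = 36 day combinations. Those beyond 30 days, for EOT on Days 332 to 340 in turn, are 4 + 4 + 4 + 4 + 3 + 2 + 1 + 0 + 0 = 22, or 61% of combinations. This again counts days, not visits.

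**5. EOT read as a last dose on Day 335 (assumption).** Visit 15 has trough measurements taken before the morning dose, so a last dose on the previous day is plausible, but no text states it. The permitted days become 31, 32, 33 and 34, and all four are beyond the limit.

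**6. Early stopper whose EOS is timed from the EOT visit (assumption).** The latest EOS is 7 + 30 + 3 = 40 days after the last dose.

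**7. Effect of moving the limit to EOT + 33.**
- Case 2: all four days are covered.
- Case 5: three of four (day 34 stays out).
- Case 4: the combinations still beyond the limit are 4 + 3 + 2 + 1 = 10 of 36.

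Three extra days are therefore enough only if EOS is counted from the same EOT as the limit, which is why EOT must be defined first.

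**The case against.** The strongest reply is that a 30-day lag looks deliberate. It matches the AE reporting period, 10.1.1 uses the same 30-day cap for gaps between study parts, and the restriction directly qualifies the sentence before it. A visit label with no upper limit can coexist with a 30-day limit on by-part counts. Much of this stands. For AE onset the limit is consistent with collection and should stay. It does not settle scheduled laboratory assessments, because their own visit window begins where the limit ends.

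A reader might infer that most EOS safety data are lost. The documents do not support that:
- Three of four permitted days is not three of four visits, and the target day itself is within the limit. The 75% cannot be applied to the 300 or more subjects expected to complete (SAP 2.1).
- Laboratory changes, weight and pulse have by-visit summaries planned up to EOS. (Table 5 names only Weeks 40, 44 and 48 for DB-WD laboratory values, a separate mismatch with 7.3.2.) No by-part abnormality count is planned for weight or pulse.
- UACR is modelled only to Week 48, EOS has no efficacy window, positive pregnancy tests are reported, and all safety data are listed.

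Nor is EOS the only check off aprocitentan. Subjects re-randomized to placebo have laboratory tests at Weeks 40, 44 and 48, and early stoppers have an EOT visit after the last dose.

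Cases 4 to 6 in the working are assumptions. Of the protocol, only the COVID-19 addendum is at hand; protocol Version 3 may state how EOS is timed.

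**Conclusion.** The point holds for scheduled EOS laboratory assessments in the by-part marked-abnormality tables. With EOT on target, three of the four permitted EOS days fall beyond the limit, so whether an abnormality first seen at EOS is counted depends on which compliant day the visit fell. If EOT means a last dose taken the day before Visit 15, none of the four days qualifies. Table 6's open window does not repair this. For subjects who were not re-randomized, WD day is undefined (10.1.2), so the EOS row's lower limit cannot be applied to them at all.

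The share of visits affected is unknown. The result rests on reading the Table 2 window as EOT + 30 to EOT + 33, which needs EOT at Day 336 or EOS counted from EOT. The primary and key secondary analyses and the AE tables are unaffected. This is a safety-counting rule that should be corrected, not evidence that EOS data are missing from the report.

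**What to change.** 1. In 10.1.1 and 7.1.1.1, state whether EOT in the 30-day rule is the last dose or the EOT visit, and from which of the two EOS is timed.
2. Keep EOT + 30 for AE onset.
3. For scheduled EOS laboratory assessments, extend the limit in both sections to cover the permitted EOS window: at least the +3 days, and more only if EOS is timed from an EOT visit that follows the last dose. The 40 days in case 6 is the outer bound under that assumption, not a default.
4. Give the EOS row of Table 6 the same upper limit, and say how it applies to subjects without a WD day.
5. Bring Table 5 into line with 7.3.2 on whether DB-WD laboratory summaries include EOS.

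The cost is a few sentences and one date condition in the programs, with no change to trial conduct. The downside is small: AE onset and scheduled laboratory assessments would have different limits, and a few assessments taken some days later would count as treatment-emergent. A simple count of EOS laboratory visits by day after EOT would show how many subjects are concerned.
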